### 599 2.4 Analysis

The original analytic plan called for aggregating each clinic's data into 8 separate return rates (one each for subgroup defined by age (50-64 vs. 65+), gender and race (minority vs. non-minority). The resulting analytic dataset would thus consist of 208 observations (26 clinics X 8 observations per clinic). Treating the resulting proportions as approximately normally distributed, we planned to use mixed model ANCOVA to estimate the screening probabilities as a function of intervention, age, gender, race, and baseline clinic screening rate, with clinic specified as a cluster variable.

- 606 607 Once the analytic cohort was accrued, we discovered that some of the clinic subgroups were extremely 608 small, which in turned threatened the validity of the planned analysis. In consultation with the NIH 609 Collaboratory's Biostatistics Core, we therefore shifted to a patient level analysis. In order to maintain the 610 initial focus on clinic-level differences, we weighted each individual by 1/(clinic size). This shift in analytic 611 plan therefore maintained the spirit of the original analysis while providing a better fit to the nature of the 612 data (i.e., a logistic model reflecting the binary nature of individual observations). An added bonus of this 613 revised analytic framework is that it allowed for a finer adjustment for patient-level factors as part of 614 secondary analyses.
- 615
- 616 In addition to the above change, we also added some sensitivity analyses to try to account for the startup
- 617 delays that were experienced. Finally, we decided to adjust for Health Center in place of other clinic-level
- 618 covariates since preliminary analyses indicated that this substantially reduced the intraclass correlation
- 619 coefficient compared to other adjustment options.

625

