### 621 **2.4.1** Primary and Secondary Outcome Analysis

The data can be viewed as coming from a 2-level hierarchical model with patients clustered within clinics,
and our primary interest is focused on clinic-level effects (to what extent did the intervention increase
clinic-level FIT/FOBT completion rates).

626 Primary Analysis

627 To assess our primary outcome, we fit generalized estimating equations (GEE) models with a logistic link to 628 model patient-level data. Patients are weighted by 1/(clinic size), so that each clinic's data will have an 629 equal weight. The primary analytic model adjusted for age, gender and health center, used robust variance 630 estimators, and specified clinic as a clustering variable to account for intra-clinic correlation. (The intra-631 class correlation coefficient for this adjusted model was 0.05.) We report the intervention effect as the 632 absolute difference between intervention and usual care clinics in adjusted probabilities calculated using 633 mean values for all covariates in the model since we felt this was the more relevant metric from a public 634 health perspective. However, we report (two-sided) p-values based on the ln (odds ratio). A p-vlaue < 0.05 635 is considered statistically significant.

636

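### The headline risk difference is predicted at mean covariate values, so it is not the equally weighted average of clinic-level differences in which the plan states its interest

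*Protocol*

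**What the plan says.** Protocol section 2.4.1 puts its interest at the level of the clinic: "and our primary interest is focused on clinic-level effects (to what extent did the intervention increase" clinic completion rates. The weighting follows from that: "Patients are weighted by 1/(clinic size), so that each clinic's data will have an" equal weight. The model is a logistic GEE, described thus: "The primary analytic model adjusted for age, gender and health center, used robust variance" estimation and clinic as the cluster.

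The effect is reported as the "absolute difference between intervention and usual care clinics in adjusted probabilities calculated using" "mean values for all covariates in the model since we felt this was the more relevant metric from a public" health viewpoint. The two-sided p-value comes from the log odds ratio. Section 2.4 explains why Health Center is in the model: "preliminary analyses indicated that this substantially reduced the intraclass correlation" coefficient compared with other adjustment options. The protocol does not describe averaging predictions over patients or clinics. It also does not say how Health Center is coded, or whether the covariate means carry the 1/(clinic size) weights.

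**The concern.** Health Center is one of the covariates set to its mean. With eight centers it can sensibly enter only as a set of indicators, and the mean of an indicator is a fraction. If clinics count equally, the clinic counts in section 1.11 give 6/26 = 0.23 for Health Center 5 and 2/26 = 0.08 for Health Center 1. The predicted probability then belongs to a composite patient who is partly in every center.

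On a linear scale this would not matter. On the logit scale, the probability at the mean linear predictor differs from the mean probability. The weights in the estimating equations do not cure this, because the mismatch arises afterwards, at prediction.

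At stake are the headline difference and the two adjusted arm rates, which readers will set beside observed clinic rates. Section 2.4.1 fixes this choice explicitly, and section 2.4.1 (Secondary Analyses) carries the same approach over to any CRC screening.

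**Working it through.** The plan gives no figure for this gap, so there is none to reproduce. The check asks what the at-means method returns when the true average clinic-level difference is known.

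**Inputs from the protocol.** Eight Health Centers (section 1.11). Usual care rates of 5%, 10% and 15% and differences of 10 to 14 points (section 2.5). A logistic model with one common intervention effect (section 2.4.1).

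**Assumed input.** The SD of the Health Center effects on the logit scale is not given, so 0.25 to 1.0 is used. The reported ICC of 0.05 cannot supply it, because that is the clinic correlation left after Health Center adjustment.

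**Formulas.** Let center h have logit a + u_h under usual care and a + b + u_h under intervention, with the u_h averaging zero. The u_h are normal quantiles at (h − 0.5)/8, rescaled to the chosen SD.
- Averaged rates: mean of expit(a + u_h), and mean of expit(a + b + u_h). Solve a and b so that these equal the planning rates.
- At-means rates: expit(a) and expit(a + b).

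**One case in full: 20% vs 10%, SD 0.8.** Here u_h = ±0.137, ±0.424, ±0.770, ±1.330, a = −2.441 and a + b = −1.568.
- Usual care by center (%): 2.3, 3.9, 5.4, 7.1, 9.1, 11.7, 15.8, 24.8; mean 10.0.
- Intervention by center (%): 5.2, 8.8, 12.0, 15.4, 19.3, 24.2, 31.0, 44.1; mean 20.0.
- Average difference: 10.0 points.
- At means: expit(−2.441) = 8.0% and expit(−1.568) = 17.2%, a difference of 9.2 points.

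**All cases** (differences taken before rounding):

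| True rates | SD | a | a + b | Usual care at means (%) | Intervention at means (%) | Difference (points) |
|---|---|---|---|---|---|---|
| 10% → 20% | 0.25 | −2.222 | −1.405 | 9.78 | 19.70 | 9.93 |
| | 0.5 | −2.295 | −1.460 | 9.15 | 18.85 | 9.70 |
| | 0.8 | −2.441 | −1.568 | 8.01 | 17.25 | 9.24 |
| | 1.0 | −2.569 | −1.662 | 7.12 | 15.95 | 8.83 |
| 5% → 15% | 0.25 | −2.972 | −1.756 | 4.87 | 14.72 | 9.86 |
| | 0.5 | −3.055 | −1.820 | 4.50 | 13.94 | 9.44 |
| | 0.8 | −3.219 | −1.947 | 3.84 | 12.49 | 8.64 |
| | 1.0 | −3.364 | −2.058 | 3.34 | 11.32 | 7.98 |
| 15% → 28% | 0.25 | −1.756 | −0.958 | 14.72 | 27.73 | 13.00 |
| | 0.5 | −1.820 | −0.998 | 13.94 | 26.93 | 12.99 |
| | 0.8 | −1.947 | −1.077 | 12.49 | 25.41 | 12.92 |
| | 1.0 | −2.058 | −1.145 | 11.32 | 24.13 | 12.81 |

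**Robustness.** The centers were also weighted by their actual clinic counts (2, 3, 3, 4, 6, 2, 4, 2), with the intercepts assigned to centers in 500 ways. For 20% vs 10% this gives 9.9, 9.7, 9.3 and 8.9 points at SDs of 0.25, 0.5, 0.75 and 1.0. Individual assignments at SD 1.0 run from 8.2 to 9.3. For 28% vs 15% at SD 1.0 the average is 12.8, with individual assignments from 12.3 to 13.2. Age and gender, at an assumed joint logit SD of 0.1 to 0.3, move a 10-point difference by about 0.1 point or less. The gap therefore comes mainly from Health Center.

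**The case against.** Prediction at covariate means is a recognised summary, the protocol states it openly, and nothing in the document contradicts it. An interest in how far clinic rates rose is not literally a promise to report the arithmetic mean of clinic risk differences. These points stand as far as they go: the method is not an error in itself, and the issue is its fit to the stated target.

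The size rests on a spread that the documents do not give. That Health Center adjustment lowered the ICC shows that centers differ, but not by how much. At an SD of 0.25 the gap is 0.1 point, and at 28% vs 15% it almost vanishes at any SD tried. This stands too and limits the weight of the point.

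Indicator coding is an inference. No other coding of eight centers makes sense, but the protocol does not state it.

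A reader might go further and infer that the primary result is invalid or exaggerated, or that the adjusted rates describe no real population. The documents do not support this. The test uses the log odds ratio and does not depend on where probabilities are evaluated. In the tabulated cases the at-means difference equals or understates the average. The result remains a legitimate prediction for a patient with average covariates.

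**Conclusion.** The point holds as a mismatch between the reported measure and the stated target, and its practical weight is low. At the planning rates, the difference moves by about 0.6 points or less when the Health Center logit SD is 0.5 or less. At SD 1.0 it moves by about 1 to 2 points when usual care is 5 to 10%. At 15% vs 28% the gap is 0.2 points or less with the centers evenly spread. The arm rates move more: a usual care rate of 10% is shown as 9.2% at SD 0.5 and 7.1% at SD 1.0.

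These figures assume a common odds ratio, indicator coding and a spread that only the trial data can supply. Hypothesis testing and the choice of an absolute scale are untouched.

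**What to change.** From the same fitted model:
1. Predict each patient's probability under intervention and again under usual care, keeping that patient's own age, gender and Health Center.
2. Average each set with the 1/(clinic size) weights.
3. Report the two standardised arm rates and their difference, with a cluster-robust delta-method or cluster-bootstrap interval. Do the same for any CRC screening.

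Keep the at-means figure beside it, label it as a prediction at mean covariates, and state whether those means were weighted.

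The computing cost is one post-estimation step without a refit. There is a small downside: sections 2.4 and 2.4.1 describe the cohort as accrued and the model as fitted, so adding this measure must be disclosed as a change made after fitting.

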### 637 Secondary Analyses

638 We used the same analytic approach for the secondary outcome of any CRC screening. For both FIT

- 639 completion and any CRC screening, additional models were fit using interaction terms to test the extent to
- which the intervention effect differed across Health Centers. The interactions were treated as fixed effectsin these models.
- 642

643 The analysis of our other secondary outcomes will be more descriptive in nature. Regarding the proportion 644 of returned FOBT/FIT kits that turn out positive, while we anticipate a sizeable number of returned 645 FOBT/FIT kits for each of the intervention clinic (typically in excess of 150), the numbers will be much 646 smaller for control clinics (for many of the smaller clinics less than 20) and hence much less precisely 647 measured. The situation is only compounded for the secondary outcomes of referral for a positive FIT and 648 completion of a colonoscopy following referral, since they are further limited to FOBT/FIT kits that are 649 returned and are positive. Hence, for all these outcomes, the focus will be more on the experience of the 650 intervention clinics than formal comparisons between intervention and control clinics, though we will look 651 at this latter question to the extent we are able. Ultimately, we wish to know the extent to which the 652 clinics are able to maintain the program and the impact it may have on their operations, and hope that this 653 information will help to shed light on this issue.

654

For the NQF scores, the data can be interpreted as coming from a step wedge design. In the year prior to
randomization all clinics were following usual care. In the first-year post randomization the intervention
clinics were using the intervention and the control clinics still usual care. In the second-year post
intervention all clinics were using the intervention. In each case we have a single observation per clinic.

659 We will use a random effects model to assess intervention effects while adjusting for within clinic

- 660 clustering. The model will allow for period effects and will also estimate separate effects for the first and
- 661 second year of intervention rollout.
- 662
- 663 Sensitivity Analyses

664 Sensitivity analysis will include GEE models without weighting, GEE models that also adjust for insurance 665 status, random effects models, and models excluding the two clinics (one intervention and one control)

- 666 affiliated with an academic medical center (these clinics did not have shared governance and did not use 667 the same FIT kit throughout the intervention).
- 668

669 Finally, while our primary analysis will include all individuals accrued after EHR tools were provided to

670 clinics on February 4, 2014, no clinic began printing letters until at least June of 2014; some did not begin

671 until spring of 2015. To account for this implementation delay, we will repeat the above analyses for FIT

- 672 completion and "any CRC screening" using a lagged dataset that only included individuals accrued between
- 573 June 4, 2014 and February 3, 2015. As with the primary dataset, outcomes for this lagged dataset will be
- assessed through August 3, 2015, after which materials were made available to usual care clinics.
- 675

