### 392 1.11.1 Clinic eligibility criteria

393 We selected these clinics by working with our advisory board to establish criteria for clinic participation.

- 394 Below is a list of these criteria. These criteria are listed below.
- 395

Clinic Criteria	Description
Clinic site size	A clinic site must have 450+ patients aged 50 - 74
Number of clinic sites in organization	Clinic organization must have at least 2 sites that meet size requirement.
FOBT/FIT	Clinic organization must use the same screening method in its intervention and usual care clinics.
Colonoscopy capacity	Clinic must have sufficient capacity to perform colonoscopies for patients who screen positive on FOBT/FIT.
Lab interface/ capacity	Clinic sites must have direct electronic interface with lab that processes FOBT/FITs; lab must have sufficient capacity to process additional tests.
Randomization	Clinics must agree to randomize their clinics; each organization will be assigned at least one intervention and one usual care site.
Testing the uninsured	Clinic organization must have a plan for screening for uninsured patients.
Research requirements	Clinic organizations must consent to leadership requirements (clinic interviews, data validation, advisory board involvement, interpretation of findings)
Prioritization/ willingness	Clinic leadership must prioritize project and set improvement targets.
Human Subjects requirements	Clinic organization must agree to cede to KP NW IRB.
Federal Wide Assurance	Clinic organizations must maintain active FWAs

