### 476 **2.2. Randomization**

477 Based on simulation work conducted by the Collaboratory's Biostatistics Core, we abandoned our original

478 plans to conduct a constrained randomization and instead opted for a simple stratified randomization

based on Health Center. Within each of these administrative units, the randomization was blocked to

480 assure maximum possible balance of intervention and control clinics. Having created the basic

- randomization scheme with two groups (A and B), the assignment of the groups to intervention and control
- 482 conditions was performed randomly on a conference call with all health center representatives on February
- 4th, 2014 to assure maximum transparency of the process to our participating sites. The randomization
   process relied on an electronic dice that was rolled by a member of the advisory board.
- 485

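### On its natural reading the intervention-by-Health-Center test is a robust Wald test with a single clinic in 8 of 16 cells, so its p-value says nothing about heterogeneity

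*Protocol*

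**What the plan says.** Section 2.4.1 sets the primary model: "we fit generalized estimating equations (GEE) models with a logistic link to" patient-level data, with weights of one over clinic size. "The primary analytic model adjusted for age, gender and health center, used robust variance" estimators, and it "specified clinic as a clustering variable to account for intra-clinic correlation". Two-sided p-values come from the log odds ratio.

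Under Secondary Analyses the same approach serves any CRC screening. For both FIT completion and any CRC screening, further models use interaction terms to test the extent to "which the intervention effect differed across Health Centers", with the interactions as fixed effects. The sensitivity paragraph repeats the analyses of both outcomes on the lagged dataset. Section 2.4.3 refers back to this Health Center analysis and then chooses random effects in place of GEE for patient-level moderators, which supports reading the Health Center test as a GEE.

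The layout comes from three places. The table in 1.11 lists 2, 3, 3, 4, 6, 2, 4 and 2 participating clinics. Section 1.11.1 states that "each organization will be assigned at least one intervention and one usual care site". Section 2.2 states: "Within each of these administrative units, the randomization was blocked to" give the best achievable balance between arms. No section names the test statistic for the interaction or a small-sample correction.

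**The concern.** A cluster-robust variance learns about clinic-to-clinic variation from the spread of clinic residuals around the fitted values. Once every Health-Center-by-arm cell has its own parameter, a cell with one clinic is fitted to that clinic's own rate. Its residual total is zero, and the sandwich records no uncertainty for it. Real differences between two clinics are then credited to the intervention effect in that Health Center, with almost no error attached.

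At stake is a false statement that the program works differently in different Health Centers. The test serves two outcomes and their lagged repeats, and such a statement could colour conclusions about maintenance and spread, which Secondary Aim 1 addresses.

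**Working it through.** **Layout.** The plan gives no figure for the interaction test; the figure that can be reproduced is the number of clinics: 2+3+3+4+6+2+4+2 = 26. The most balanced splits are 1/1, 2/1, 2/1, 2/2, 3/3, 1/1, 2/2, 1/1 for Health Centers 1 to 8. Single-clinic cells: 3 × 2 + 2 × 1 = 8 of 16, whichever arm receives the extra clinic in Health Centers 2 and 3. Residual between-clinic df: 26 − 16 = 10, all from Health Centers 2, 3, 4, 5 and 7 (1+1+2+4+2).

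**Algebra, without covariates.** In a cell with k clinics the clinic score totals sum to zero. With k = 1 the only total is zero. More generally, with clinics of equal size, the expected sandwich variance of a cell's logit is the true variance times (k − 1)/k, which gives 0, 1/2 and 2/3 for k = 1, 2 and 3. The 7 × 7 interaction covariance has rank 5 at most, and contrasts among Health Centers 1, 6 and 8 have a robust SE of exactly 0. Age and gender terms leave only a trace of variance.

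**Size.** Inputs: ICC .05 (2.4.1) and 450 patients per clinic (2.5). Assumptions: the ICC is on the logit scale, so σ² = (.05/.95) × π²/3 = 0.173 (clinic SD about 0.42), and the average p(1 − p) is 0.12, so binomial variance is 1/(450 × 0.12) = 0.0185. Per-clinic variance is 0.173 + 0.0185 = 0.192. For arms with a and b clinics:

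- true SD of ln(OR) = √[0.192 × (1/a + 1/b)]
- root expected sandwich variance = √[0.192 × ((a − 1)/a² + (b − 1)/b²)]

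| Split | Health Centers | True SD | Root expected sandwich variance | Simulated median robust SE, with age and gender |
|---|---|---|---|---|
| 1/1 | 1, 6, 8 | 0.62 | 0 | about 0.002 |
| 2/1 | 2, 3 | 0.54 | 0.22 | 0.15 to 0.16 |
| 2/2 | 4, 7 | 0.44 | 0.31 | 0.24 to 0.26 |
| 3/3 | 5 | 0.36 | 0.29 | 0.26 |

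Simulated medians lie below the root expectation because variances estimated on so few df are skewed.

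The document does not give the scale of the ICC, so the 1/1 value needs a range. No clinic variance: √(2 × 0.0185) = 0.19. Clinic SD 0.75: √[2 × (0.5625 + 0.0185)] = 1.08.

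**Simulation with no interaction.** Weighted logistic GEE, clinic as cluster, age, gender, Health Center, arm and Health Center by arm. Assumptions: usual care 10%, common OR 2.3 (about +10 points), clinic SD 0, 0.42 or 0.6, 450 to 2000 patients per clinic, independence and exchangeable working correlation, 150 to 300 runs per setting.

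- 7-df robust Wald test at 5%: rejected in 100% of runs in every covariate-adjusted setting, including zero clinic variance. The median statistic was about 12,000 to 210,000, against a critical value of 14.07. A standard GEE package rejected in 30 of 30.
- No covariates, generalized inverse: 96%.
- Only Health Centers 4, 5 and 7 (at least two clinics per arm): 34%, so the single-clinic cells are the main fault but not the only one.
- Generalized score test, same model: 3% to 10%.
- Clinic-level F on 7 and 10 df: 5% to 8%. With 150 runs the Monte Carlo SE at 5% is √(.05 × .95/150) = 1.8 points.

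**The case against.** The strongest objection is that the document names no test statistic for the interaction. A reader might infer that a fixed-interaction GEE must reject in this layout. The documents do not support that: a generalized score test on the same model rejects in 3% to 10% of null runs. This stands, and it limits the claim to the robust Wald test. That remains the natural reading, since 2.4.1 pairs robust variance with p-values on ln(OR) and mentions neither a score test nor a small-sample correction.

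A reader might also infer that the robust variance vanishes everywhere. It nearly vanishes only in Health Centers 1, 6 and 8; in the other five it is too small. Nor does the plan promise Health-Center-specific estimates with intervals: 2.4.1 promises only the test, so misleadingly narrow intervals are a risk to head off and not a planned output.

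The listed sensitivity analyses include random effects models and exclusion of the two academic-affiliated clinics. They mitigate at most. The text does not tie either to the interaction test, and if those two clinics form one of the 1-versus-1 Health Centers, two such Health Centers remain.

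Finally, this is a secondary test. Aim 1 gives age, sex, insurance and Hispanic ethnicity/race as examples of its subgroups, and Health Center is not among them. That is fair and sets the severity.

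**Conclusion.** The defect is real on the natural reading. With a robust Wald test the interaction p-value is uninformative for FIT completion, any CRC screening and the lagged repeats, because it rejects in essentially 100% of datasets without heterogeneity. The count of 8 single-clinic cells in 16 follows from the document alone. The true SD in the 1-versus-1 Health Centers, about 0.6 to 1.1, depends on the assumed clinic variance, but rejection does not: it was complete even with no clinic variance.

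It would be wrong to conclude that the main trial result is compromised. The primary model has no interaction terms, and its effect estimate is not affected by this point. Should-fix.

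**What to change.** State in 2.4.1 that the robust Wald test is not used for the intervention-by-Health-Center interaction, and name one of these instead:

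- a clinic-level F test on 7 and 10 df, for example on clinic empirical logits;
- a generalized score test, or a permutation test built around the common effect, either of which keeps the patient-level model;
- a descriptive display of Health Center differences without a p-value.

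Add that no GEE robust interval is attached to any Health-Center-specific effect; changing the test alone would not repair such intervals. Apply the same choice to both outcomes and the lagged dataset.

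The cost is a few sentences and a small re-analysis. A valid test here has low power, because only 10 df carry information on clinic variation. The clinic-level version also drops the age and gender adjustment unless covariate-adjusted clinic rates are used, and it steps back from the patient-level framework adopted in 2.4; the score or permutation test avoids that.

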# • Codes for FOBT/FIT

screening

Code	Description
82270	Occult blood by perox activity, 1.3 spec (82270)
82271	Blood, occult, by perox activity (guaiac)
82272	Blood, occult, by perox activity (guaiac)
82274	Fecal globin by immunochemistry
G0328	Assay test for blood, fecal
G0394	Blood occult test (eg. Guaiac) feces, for single determination for colorectal neoplasm (i.e., patient was provided 3 cards or single triple care for consecutive collection)
LP1081	Fecal globin by immunochemistry (Medicare)
LP1398	Fecal occult blood x3 (ncnm lab)
LP926	Occult blood, stool, guaiac x3
LS652	Occult blood, fecal, immunoassay
LS885	Hemoccult/guaiac (colorectal) screen (82270)
LS900	Occult blood stool monoclonal 1
LS901	Occult blood stool monoclonal 2
LS 902	Occult blood stool monoclonal 3
LS912	Occult blood stool monoclonal x3
LS932	Guaiac heme in house (AHTMG)
LS944	Occult blood, series, first spec
LS945	Series occult blood third specimen
Ls990	Occult blood, series, second spec
LS992	Occult blood stool x1 (lab)
LV1433	FOBT waived, immunochemical
LV1542	Occult blood/hemoccult (88272)
LV1576	HP-lab-occult blood (Tahoe Forest)
LV1684	Fecal global by immunochemistry (POCT) 82274
LV1687	Occult blood, fecal, immunoassay, third spec
LV1737	Fecal occult by immunochemistry (82274) POCT
LV414	Fecal globin by immunochemistry (Medicare)
LV472	Occult blood (MTY in-house)
LV510	Stool occult blood, in-house (82270)

[figure not shown]
LV705	Hemoccult/iFOB test
LV877	Stool occult blood (CHC in -house)
LV908	Fecal globin- in house (Bend only)
LV919	Fecal occult blood x1 (NCNM lab)
LX063	Occult blood, stool (diagnostic)

• Codes for Flexible Sigmoidoscopy

educitor rexiste signification of the second s		
Code	Description	
45330	Diagnostic sigmoidoscopy	
45331	Sigmoidoscopy and biopsy	
45332	Sigmoidoscopy, flexible; w/removal, fb	
45333	Sigmoidoscopy, flexible; w/removal, lesion, hot forceps/cautery	
45334	Sigmoidoscopy, flexible; w/control, bleeding	
45335	Sigmoidoscopy, flexible; w/directed submucosal injections, any substance	
45337	Sigmoidoscopy, flexible; w/decompression, volvulous, any method	
45338	Sigmoidoscopy, flexible; w/removal, lesion, snare	
45339	Sigmoidoscopy, flexible; w/ablation, lesion, not removed by hot forceps/cautery/snare	
45340	Sigmoidoscopy, flexible; w/dilation, balloon, 1-> strictures	
45341	Sigmoidoscopy, flexible; w/endoscopic ultrasound exam	
45342	Sigmoidoscopy, flexible; w/transendoscopic ultrasound guided intra- transmural fine needle aspiration/bx	

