## 505 2.3.2 Secondary Outcomes

[figure not shown]
- 506 Our secondary outcomes are provided below:
- For participants who received a FIT kit, the probability of returning it within 3, 6, 9 and 12 months of its being sent as well as time to FIT/FOBT return
   Receipt of any CRC screening (fecal test, sigmoidoscopy or colonoscopy) during the follow-
  - NQF score (proportion of those age 50-74 with a colonoscopy within 10 years, flexible
  - sigmoidoscopy within 5 years, and FOBT/FIT within 1 year) as assessed relative to the oneyear pre and each of the first two years post randomization
    - Presence of a positive FIT/FOBT among those who return a FIT kit
    - Referral for a colonoscopy among those with a positive FIT/FOBT
    - Completion of a colonoscopy following a positive FIT/FOBT

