## 690 **2.5. Power and Sample Size**

For Phase 2, STOP effectiveness will be assessed using a two-arm, cluster randomized design with a total of26 clinics. Our power calculations are based on the following assumptions:

- We have equal Ns per clinic and equal numbers of clinics per group. In practice, the sample sizes will not be equal, but since almost all clinics had at least 450 subjects who qualified for the intervention (most had at least 700 qualifying individuals), we conservatively use this figure for all sites.
- We compare two binomial proportions with a type I error rate of 5%. For each of a variety of
   design assumptions, we determined the design effect due to clustering and used this to calculate
   the effective sample size as if these were independent observations. We then used the formulas
   from Hulley et al., to estimate power.
- Finally, we assume an intention-to-treat approach in which we consider a treatment failure to be any individual who receives the initial intervention mailing (or for the UC clinics would have qualified to receive the mailing) and does not have a completed fecal test within their follow-up window. Although we expect to learn through the intervention process that many intervention participants do not require screening, we have no way to exclude comparable individuals from the control clinics and hence must ignore this information for the primary analysis.
- 709
  710 We calculated power for Intra-class Correlation Coefficients (ICCs) of .03, .04, and .05, usual care FIT return
  711 probabilities of 5%, 10%, and 15%, and intervention effects (absolute differences) of 10 14 percentage

- points. Based on analyses done by [name] (STOP co-PI), we expected the ICC to be about .03, though as
  it turned out the ICC was closer to .05. Using this latter figure, we had >90% power for detecting effect
  sizes of at least 13 percentage points even with UC probabilities as high as 15%. Power was > 88% for
  detecting effect sizes of at least 11 percentage points if the UC probabilities were no higher than 10%.
  Power declines only slightly even for subgroups 1/6th of the full cohort (e.g., for 17% Hispanic patients).
- 717 This reflects the fact that we have an overabundance of individuals within each clinic and that the main
- 718 driver of power is thus the number of clinics.
- 719

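### Any between-arm look at positive tests, referral and colonoscopy completion uses groups selected after randomization, and the plan cautions only about precision

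*Protocol*

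**What the plan says.** Protocol section 2.3.2 lists three outcomes downstream of the fecal test: "Presence of a positive FIT/FOBT among those who return a FIT kit"; "Referral for a colonoscopy among those with a positive FIT/FOBT"; and "Completion of a colonoscopy following a positive FIT/FOBT".

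Section 2.4.1, Secondary Analyses, sets the status of everything after the any-CRC-screening outcome: "The analysis of our other secondary outcomes will be more descriptive in nature". It expects typically more than 150 returned kits per intervention clinic, but fewer than 20 in many of the smaller control clinics. It adds that the sparseness is worse for referral and for "completion of a colonoscopy following referral, since they are further limited to FOBT/FIT kits that are" returned and positive. It therefore puts more weight on the experience of "intervention clinics than formal comparisons between intervention and control clinics, though we will look" at that second question as far as the team is able.

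So a between-arm look stays open, no model or test is fixed for it, and the one reason given for caution is imprecision in the control clinics. No version of these three outcomes over all accrued patients is set out.

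**The concern.** Membership of the denominators is decided after randomization, by the behaviour that the program acts on. Returners in usual care are people who complete a test without the mailing. Returners in intervention clinics are a mixture of such people and others who return only because a kit was mailed. If the two kinds differ in risk of a positive test or in readiness to complete a colonoscopy, the arms will differ on these proportions even when the program changes nothing after the test.

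The stated caution points readers the wrong way. If imprecision were the only obstacle, a larger control sample would make the comparison sound, but sample size does not remove selection. These outcomes show whether extra tests turn into completed work-ups, so an unguarded contrast could make a useful program look harmful, or flatter a weak one.

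Section 2.5 applies the relevant principle to the primary analysis: it ignores information learned only through the intervention, because comparable control patients cannot be identified. Nothing carries that principle over to the three downstream outcomes.

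**Working it through.** The plan states no figure on this point, so there is none to reproduce. The check has four parts.

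**1. How far the returner groups differ in make-up.** Section 2.5 uses usual-care return of 5%, 10% and 15% and absolute effects of 10 to 14 points. Assume that everyone who would return under usual care would also return under the program. The mailing-induced share of intervention returners is then effect / (usual-care rate + effect).
- Lowest: 10 / (15 + 10) = 40%.
- Highest: 14 / (5 + 14) = 74%.
- Mid case (10%, 11 points): 11 / 21 = 52%.

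**2. What that can do to completion among positives.** Let u and v be the usual-care and intervention return rates. Assume 8% positivity throughout, and completion after a positive test of a in patients who return either way and b in mailing-induced returners. The program has no effect on care after a positive test. Usual care then shows a, and intervention shows [u·a + (v − u)·b] / v. Positivity, a and b are assumptions; the documents give none.
- Mid case, u = 10%, v = 21%, a = 60%, b = 40%: (0.10 × 0.60 + 0.11 × 0.40) / 0.21 = 49.5%, against 60% in usual care.
- Completed colonoscopies per 1,000 accrued, same case: 1,000 × 0.08 × 0.10 × 0.60 = 4.8 in usual care, and 1,000 × 0.08 × (0.060 + 0.044) = 8.3 in intervention.
- Over return pairs 5/15, 10/20, 10/21 and 15/28%, the conditional difference is −9.3 to −13.3 points.
- With a = b it is 0.
- With a = 40% and b = 60% it is +9.3 to +13.3 points.

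**3. Positivity among returners.** With an assumed 10% positivity in patients who return either way and 6% in mailing-induced returners, the same four return pairs give 10% in usual care against 7.3% to 8.1% in intervention, with no effect on disease. In the mid case, positives per 1,000 accrued are 10.0 against 1,000 × (0.10 × 0.10 + 0.11 × 0.06) = 16.6.

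**4. Precision.** Section 2.5 works with 450 patients per clinic and 26 clinics in equal groups, so 13 × 450 = 5,850 per arm. Pooled usual-care tests at 5% to 15% are 293 to 878. Positives are far fewer. In the mid case there are 585 tests, and assumed positivity of 7.0% to 9.5% gives about 41 to 56 positives, or 3 to 4 per clinic.

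For positives per accrued patient, those usual-care rates are 7.0 and 9.5 per 1,000. Adding 11 points of mailing-induced returns at an assumed 5% positivity (5.5 per 1,000) gives 12.5 and 15.0 in intervention. With n = 5,850 / (1 + 449 × ICC), a two-sided 5% test of two proportions has this power:

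| Assumed ICC | Effective n per arm | 7.0 vs 12.5 | 9.5 vs 15.0 |
|---|---|---|---|
| 0 | 5,850 | 86% | 77% |
| 0.002 | 3,082 | 59% | 50% |
| 0.01 | 1,066 | 25% | 21% |

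For completed colonoscopies (4.8 vs 8.3 per 1,000, from part 2) the same formula gives about 40% at ICC 0.002 and 17% at 0.01. The documents give no ICC for these outcomes; their 0.05 is for FIT completion.

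**The case against.** The best reply is that the plan already holds back. Section 2.4.1 calls these outcomes descriptive, centres them on the intervention clinics, and says their purpose is to learn whether clinics can sustain the program and what it does to their operations. Proportions among returners and positives serve that purpose well. Effects over all accrued patients are already modelled for FIT completion and for any CRC screening, which includes colonoscopy. This stands, and it limits the point to the between-arm look that is left open.

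Three stronger readings are tempting, and the documents do not support them.
- *That the arms are set to be formally compared on these outcomes.* They are not; no model, test or p-value is planned for them.
- *That usual-care tests are known to be symptom-driven, because the code list contains* "Occult blood, stool (diagnostic"*).* That list sits in section 1.4.2, among codes that satisfy Health Maintenance and so decide who is due for screening. It is not presented as the outcome definition and applies to both arms. No share of symptom-driven tests is given anywhere. The selection argument does not need it.
- *That the small-numbers caution is mistaken.* Pooled over 13 clinics it is weaker for positivity, but about 41 to 56 usual-care positives in the mid case make it a real limit for referral and completion. Precision is a second problem alongside selection.

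**Conclusion.** The point holds in a limited form. The three denominators are formed after randomization by the behaviour that the program changes, a between-arm look is kept open, and selection is not mentioned. Any such comparison can be biased and can run opposite to the effect per accrued patient.

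A reader might infer that these comparisons are certainly confounded or will make the program look worse. That goes too far. The 40% to 74% mailing-induced share follows from section 2.5's figures, given the assumption that usual-care returners would also return under the program. The size and sign of the bias rest on differences between the two kinds of returner that the documents do not give, and equal behaviour gives no bias.

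Separately, section 2.3.2 counts completion after a positive test, whereas section 2.4.1 words it as after referral. Positive patients who were never referred count in the first denominator and drop out of the second.

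The primary outcome and any-CRC-screening analyses are unaffected.

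**What to change.** In section 2.4.1:
- Make any between-arm look at these outcomes on all accrued patients: the proportion with a positive FIT/FOBT, with a positive test and a referral, and with a positive test and a completed colonoscopy. Report each by arm with clinic-clustered intervals, and use the primary model where counts allow.
- Keep the proportions among returners or positives as description, and state that they are not causal contrasts between arms because the groups are selected after randomization.
- Reconcile the completion denominator with section 2.3.2.

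The cost is a few sentences and three further result rows, built from events that these outcomes already require. The real downside is precision: events per accrued patient are rare, so intervals will be wide, and the primary model may prove fragile for completed colonoscopies. A null result on these rows should not be read as evidence of no effect.
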